## 1.0 BACKGROUND AND RATIONALE

### 1.1 Study Synopsis

Increasing the sensitivity and specificity of diagnostic imaging in patients at high risk for breast cancer could provide substantial clinical benefit by improving diagnosis, preventing over-treatment, and reducing healthcare costs. Acoustic angiography is a new type of contrast enhanced ultrasound imaging which is specifically sensitive to microvascular structure and density. It evaluates tumor micro-vasculature and may provide a powerful prognostic tool for the diagnosis of breast cancer, and eventually for treatment evaluation.

Sixty patients who are to have a clinical surgical breast biopsy based on results from pre-study standard of care (SOC) imaging will be recruited from the UNC Breast Clinic for participation in the study. The primary objective of this single arm study is to compare the sensitivity and specificity of acoustic angiography with traditional b-mode ultrasound in the distinction of malignant versus benign breast lesions. Secondary objectives include a comparison of area under the curve (AUC) for acoustic angiography versus b-mode ultrasound, comparison of radiologist preference for the two imaging techniques for each of 3 lesion characteristics, and quantification of vessel tortuosity based on acoustic angiography imaging results. These metrics will be used to develop a predictive model of malignancy which will subsequently be compared to results from radiology review.

### 1.2 Traditional Breast Cancer Screening and Diagnosis

Breast cancer is the most common cancer type among women. Approximately 10% of women in the United States develop breast cancer during their lifetime and 30% to 40% of these patients will die from it.[33, 34] Mammography is an effective tool for the early detection of breast cancer in the majority of women.[35] However, for women with dense breast tissue (considered an independent risk factor for breast cancer) and younger women, mammography performs poorly due to lower sensitivity and specificity in these groups.[37] For young women with heritable mutations who wish to begin screening at a younger age, these limitations are especially problematic.[38] Additionally, mammography is less sensitive in women who have undergone breast augmentation. Given these limitations, most of these women may undergo additional imaging with breast ultrasound or Magnetic Resonance Imaging (MRI).

MRI is time consuming, extraordinarily costly, and has limited availability, especially among rural and underserved populations. Another screening option, breast ultrasound (without contrast), is widely used when additional imaging beyond mammogram is required due to its real-time imaging

capability (>30 images per second), portability, safety (does not involve radiation), and relatively low cost compared to breast MRI. Unfortunately, while breast ultrasound is highly sensitive (96%), it is less specific (70%), resulting in a high false positive rate. This results in unnecessary biopsies with associated complications, additional follow-up and negative psychosocial impacts on patients, e.g., significant anxiety. A significant clinical need exists to improve breast ultrasound sensitivity and specificity.

### 1.3 **Angiogenesis**

Angiogenesis is the development of new microvasculature, and is well recognized to be involved in the growth of solid tumors as well as tumor invasion and metastasis. Recent studies have reported an association between microvessel density and poorer recurrence-free, cancer-specific and overall survival.[39-46]. Furthermore, both microvessel density and microvessel morphology have been reported to be associated with the clinical response to chemotherapy.[16, 47-49] However, no current clinical imaging modality can directly evaluate the microvasculature associated with suspected breast tumors.[50] Histological techniques based on core needle biopsy or surgical biopsy may evaluate only a small portion of a lesion, and require additional invasive procedures. Thus, direct non-invasive evaluation of the tumor micro-vasculature may provide a powerful prognostic tool for the diagnosis of breast cancer, and also provide a potential tool for treatment evaluation.

#### 1.3.1 **Screening Based on Angiogenesis-Acoustic Angiography**

Acoustic angiography allows for the viewing of vessel shape and delineation of 'tortuosity,' which can indicate the presence and progression of cancer. This ability to image the microvasculature depends on the use of a multi (high) frequency ultrasound scanner in addition to a traditional single-frequency pulse-echo ultrasound scanner (b-mode ultrasound), the latter to ensure accurate anatomical location of the lesion. Because of this dependence on pulse-echo, the technique is referred to as "acoustic" angiography [62].

Acoustic angiography also depends on use of an ultrasound contrast agent. Contrast enhanced ultrasound imaging has been used for nearly two decades for clinical cardiology in the United States (and is currently routinely used in UNC Hospital Cardiology Clinics), and is much more widely used in Europe and Asia for visualization of blood perfusion in organs, tissues, and tumors.[51] Early concerns about the safety of ultrasound contrast (specifically with the contrast agent (perflutren lipid; Definity®) due to events in a clinical trial have been resolved; the overwhelming amount of more recent evidence from large clinical studies has shown that contrast ultrasound is very safe.[52-54] In fact ,it is much safer than other commonly used techniques, such as coronary angiography, exercise ECG, or myocardial scintigraphy.[55] Furthermore,

it does not have the risks of nephrogenic systemic fibrosis associated with gadolinium based MRI contrast agents when used in renally compromised patients. On October 27, 2011, the FDA eliminated the requirement for patient monitoring 30 minutes after ultrasound contrast examination, based on these and other recent safety data. The ultrasound contrast agent to be used in LCCC1405 is perflutren lipid.

#### **1.4 Perflutren Lipid Background and Known Toxicities**

See <http://www.accessdata.fda.gov/scripts/cder/drugsatfda/> for full prescribing information on perflutren when used according to its FDA-approved indication. Also see section 6.1.5.

##### **1.4.1 Background and Current Indications**

Definity® (perflutren lipid) is an FDA-approved lipid-shell microbubble ultrasound (US) contrast agent that may be administered by an intravenous (IV) bolus or infusion. Currently, this contrast agent is approved for use in patients with suboptimal echocardiograms to opacify the left ventricular chamber and to improve delineation of the left ventricular endocardial border. It is not approved as a contrast agent for acoustic angiography in the breast.

When used according to its approved indication, the maximum dose of perflutren is administered as either two bolus doses or one single intravenous infusion.

For our study, perflutren lipid will be administered intravenously by a nurse or trained medical personnel (see section 4.3).

##### **1.4.2 Associated Toxicities**

In pre-market clinical trials 1716 subjects were evaluated with activated perflutren lipid. Of the 1716 subjects, 144 subjects (8.4%) had at least one treatment-related adverse reaction. There were 26 serious adverse events and 15 (0.9%) subjects discontinued because of an adverse event. Nineteen subjects (1.1%) suffered serious cardiopulmonary adverse events including eight deaths. The deaths occurred several days after activated perflutren lipid administration and appear to be related to the course of underlying disease. Of the 11 other serious adverse events, which appeared within 2-15 days of the drug administration, all appeared to be a progression of underlying cardiac and non-cardiac disease. However, a role for perflutren lipid in the initiation or course of these adverse events cannot be ruled out.

There were 15 discontinuations reported. Nine of these patients were discontinued after the first injection. One patient experienced a hypersensitivity reaction with urticaria and pruritus and all the other patients experienced dizziness, chest pain, dyspnea or back pain.

Adverse events (AEs) appeared within 1 – 15 minutes of the drug administration and were of moderate intensity resolving usually without treatment within minutes or hours after onset.

For all AEs, there were no differences in the overall incidence based on age, gender, or route of administration. The most common events were (% of patients experiencing): headache (2.3%), back and renal pain (1.2%), flushing (1.1%) and nausea (1.0%).

#### *Cardiopulmonary Reactions*

In 2007, in response to post-marketing reports of 4 deaths and 190 serious cardiopulmonary reactions, the FDA issued a black box warning for both Definity® and Optison® adding disease state contraindications and a mandatory 30 minute monitoring period following administration in all patients. Following this there have been several large scale safety studies looking into the records of a total of more than 200,000 patients who received one of these contrast agents. In all those studies a composite rate of serious adverse events was calculated to be 1 – 3 in 10,000,[22] compared to gadolinium-based MRI contrast which has an incidence of NSF of 2 – 5 in 100 patients with chronic kidney disease.[23]

Following a meeting of the FDA Cardio-renal Advisory Committee in 2008, the black box warning was revised. The revisions shortened the contraindications to include cardiac shunts and hypersensitivity to perflutren, and mandated the 30 minute monitoring period be limited to patients with pulmonary hypertension or unstable cardiopulmonary conditions. The black box warning was further revised in 2011, removing the mandatory 30 minute monitoring period, but stating that most serious cardiopulmonary reactions occur within 30 minutes of administration. For this reason, the label states that cardiopulmonary resuscitation personnel and equipment be readily available prior to perflutren administration, and that all patients be monitored for acute reactions.

Patients with a history of cardiac shunts, pulmonary hypertension or unstable cardiopulmonary conditions will be excluded from our study. In addition, all patients will be monitored for 30-minute post-perflutren administration by the research nurse or research physician.

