3.1.4 Able to provide informed consent

3.1.5 Negative urine pregnancy test in women of child-bearing potential

### 3.2 Exclusion Criteria

[figure not shown]
All subjects meeting any of the exclusion criteria at baseline will be excluded from study participation

- 3.2.1 Male (it is uncommon for men to present for imaging and the overwhelming majority of findings are non-cancerous and do not lead to biopsy; male breast cancer represents <1% of newly diagnosed breast cancer)
- 3.2.2 Institutionalized subject (prisoner or nursing home patient)
- 3.2.3 Critically ill or medically unstable and whose critical course during the observation period would be unpredictable (e.g., chronic obstructive pulmonary disease (COPD))
- 3.2.4 Known hypersensitivity to any component of perflutren lipid (Definity®)
- 3.2.5 Right to left shunt, severe pulmonary hypertension (pulmonary artery pressure >90mmHg), or adult respiratory distress syndrome
- 3.2.6 Active cardiac disease including any of the following:
- Severe congestive heart failure (class IV in accordance with the classification of the New York Heart Association)
  - Unstable angina.
  - Severe arrhythmia (i.e. ventricular tachycardia, flutter fibrillation; ventricular premature complexes occurring close to the preceding T-wave, multifocal complexes).
  - Myocardial infarction within 1 year prior to the date of proposed Definity® administration.
  - Uncontrolled systemic hypertension (systolic blood pressure (BP) >150 mm Hg and/or diastolic BP >90 mm Hg despite optimal medical management)
- 3.2.7 Any woman who is pregnant or has reason to believe she is pregnant or any woman who is lactating (the possibility of pregnancy has to be excluded by negative urine  $\beta$ -HCG results, obtained within 24 hours before the perflutren lipid administration, or on the basis of patient history, e.g.: tubal ligation, hysterectomy or a minimum of 1 year without menses)

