### **4.3 Acoustic Angiography**

#### **4.3.1 Perflutren Administration**

At the time of imaging, the contrast agent perflutren lipid (see section 4.3) will be administered. See

[http://www.definityimaging.com/pdf/VIALMIX\\_Users\\_Guide.pdf](http://www.definityimaging.com/pdf/VIALMIX_Users_Guide.pdf), and the package insert, for instructions on perflutren lipid preparation and activation. Perflutren lipid is intended for intravenous (IV) administration only after activation in the Vialmix® apparatus. Cardiopulmonary resuscitation personnel and equipment will be readily available prior to perflutren administration, and all patients will be monitored for acute reactions.

Perflutren will be administered in a single dose using a bolus administration. (see <http://www.definityimaging.com/how-administration.html>). Although the prescribing information allows for two 10 uL/kg doses separated by 30 minutes, we will be administering double the package recommended dose (administering 20 uL/kg) administered within 30-60 seconds, followed by a 10mL saline flush. No second dose will be administered. All patients will be monitored for 30-minute post-perflutren administration by the research nurse or research physician. Monitoring will include taking vitals (O2 sat, HR, RR, BP). The oxygen saturation, heart rate, and respiration rate will be monitored continuously for 30 min. The blood pressure will be monitored every 15 minutes. This study will be conducted in Mammography of the UNC Cancer Hospital, so trained medical personnel will be available as needed.

The initial concentration will be diluted, although the final dilution amount is not finalized (most likely to range from 1:1 (full dose) to - 1:5 dilution in saline). This dilution technique is still to be determined based on performance because this is a new type of imaging. We will infuse via hand bolus injection. The infusion time will be approximately 30 - 60 seconds for the dose.

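### The safety section excludes any pulmonary hypertension or cardiac shunt, but criterion 3.2.5 excludes only pulmonary artery pressure above 90 mmHg and right-to-left shunt

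*Combined protocol and SAP*

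**What the plan says.** Section 1.4.2, under Cardiopulmonary Reactions, recounts the history of the boxed warning and then commits the study to an exclusion: "Patients with a history of cardiac shunts, pulmonary hypertension or unstable cardiopulmonary conditions will be excluded from our study". It sets no limit on the severity of pulmonary hypertension, the direction of the shunt, or whether the shunt is current. The same text says the 2008 label revision kept mandatory 30-minute monitoring "limited to patients with pulmonary hypertension or unstable cardiopulmonary conditions", and that the 2011 revision removed the mandate.

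Section 3.2 opens with the rule that governs enrolment: "All subjects meeting any of the exclusion criteria at baseline will be excluded from study participation". Three of its criteria bear on this point:

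- 3.2.5: "Right to left shunt, severe pulmonary hypertension (pulmonary artery pressure >90mmHg), or adult respiratory distress syndrome".
- 3.2.3: "Critically ill or medically unstable and whose critical course during the observation period would be unpredictable", with chronic obstructive pulmonary disease as its example.
- 3.2.6: "Active cardiac disease including any of the following", followed by class IV heart failure, unstable angina, severe arrhythmia, myocardial infarction within a year, and uncontrolled systemic hypertension.

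On dose, section 4.3.1 says "we will be administering double the package recommended dose (administering 20 uL/kg) administered within 30-60 seconds". It notes that the prescribing information allows two 10 uL/kg doses 30 minutes apart.

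**The concern.** The two sections give different rules for who may receive the contrast agent. Someone reading section 1.4.2 would believe that no woman with pulmonary hypertension or a cardiac shunt is dosed. Someone screening from section 3.2 would enrol some of them.

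The disagreement concerns a group that the protocol itself singles out when it describes the label history, and the drug is given off-label as a bolus of twice the recommended single dose. Section 11.5 requires the study to be run exactly as the protocol describes, which is impossible for these women while the two texts differ. Whether enrolling one of them is compliant or a reportable departure depends on which section is consulted.

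**Working it through.** The plan states no figure on this point, so there is none to reproduce. The check compares the texts and then sizes the gap under an assumption.

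**Comparing the rules**

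| Patient | Section 1.4.2 | Section 3.2 |
|---|---|---|
| Pulmonary artery pressure above 90 mmHg | Excluded | Excluded (3.2.5) |
| Stable, known pulmonary hypertension, 90 mmHg or below | Excluded | Not excluded |
| Right-to-left shunt, including bi-directional or transient | Excluded | Excluded (plain reading of 3.2.5) |
| Left-to-right shunt only, or a past shunt | Excluded | Not excluded |
| Unstable cardiopulmonary condition | Excluded | Broadly covered (3.2.3, 3.2.6) |

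The second and fourth rows conflict. Take a stable woman with known pulmonary hypertension and a pulmonary artery pressure of 60 mmHg:

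1. 3.2.3 is not met, because she is neither critically ill nor medically unstable.
2. 3.2.5 is not met, because 60 is not above 90.
3. 3.2.6 is not met, because neither pulmonary hypertension nor shunts appear in its list.
4. She may be enrolled on this ground, although 1.4.2 says she will not be.

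**Dose**

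- Single-dose ratio: 20 / 10 = 2.0.
- Ratio to the total of the two permitted doses: 20 / (10 + 10) = 1.0.

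The bolus is double the recommended single dose but does not exceed the two-dose total.

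**Size of the gap**

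The sample size, n = 60, is from section 4.2. The share p of otherwise eligible women in the two gap rows is an assumption; the documents give no value. Expected number = 60 × p. Probability of at least one = 1 − (1 − p)^60.

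| Assumed p | Expected among 60 | Probability of at least one |
|---|---|---|
| 0.1% | 0.06 | 5.8% |
| 0.5% | 0.30 | 26.0% |
| 1% | 0.60 | 45.3% |
| 2% | 1.20 | 70.2% |

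These are chances of enrolling a woman whom 1.4.2 excludes, not chances of harm. They also suppose that screening follows section 3.2 alone.

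**The case against.** The strongest reply is that section 3 governs enrolment and the sentence in 1.4.2 is background shorthand for 3.2.3, 3.2.5 and 3.2.6. On that view the error is one over-broad sentence, and nothing in the documents shows that 3.2.5 is the wrong text. This is a fair point about which text to change, and the fix below allows for it. It does not remove the conflict: 1.4.2 is worded as a commitment and is paired with monitoring as the protocol's answer to cardiopulmonary risk. If 3.2.5 is the intended rule, 1.4.2 overstates the protection.

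A second reply is that other criteria might reach these women. The example in 3.2.3 is a chronic lung disease, and the list in 3.2.6 could be read as open-ended. But stretching either to cover milder pulmonary hypertension would make the explicit 90 mmHg threshold in 3.2.5 pointless.

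The objections about weight largely stand:

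- Every woman receives the 30-minute monitoring that the 2008 revision reserved for higher-risk patients, with resuscitation cover.
- The monitoring mandate was lifted in 2011, and the October 2011 warning summarised in 6.1.5 does not name pulmonary hypertension among the conditions that may raise risk.
- The embolization hazard in 6.1.5 concerns right-to-left, bi-directional and transient right-to-left shunts, which 3.2.5 covers. The residual shunt gap has little safety content.
- No text links dose to risk in pulmonary hypertension.
- The prevalence range is assumed and spans 20-fold.

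These limit the likely harm. They do not tell a screener which rule to apply.

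**Conclusion.** The concern holds. Both statements are current protocol text and cannot both be followed for a stable woman with known pulmonary hypertension at or below 90 mmHg or, secondarily, for one with a left-to-right or past shunt. That conclusion rests on the wording alone and needs no prevalence figure.

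Under the assumed share of 0.1% to 2%, roughly 0 to 1 of the 60 women would be affected. The safety consequence cannot be sized from the documents and is probably small. Sensitivity, specificity, the power calculation and the analysis are untouched. It should be fixed because it decides who receives the bolus and costs almost nothing to correct.

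**What to change.** Choose one rule and state it in both places.

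- **Preferred, if 1.4.2 reflects the intent:** reword 3.2.5 to exclude any known or past cardiac shunt (including bi-directional and transient right-to-left), any known pulmonary hypertension, or adult respiratory distress syndrome. Naming the shunt types only makes explicit what a plain reading already covers. Known means from history and records, so no new test is required.
- **If the sponsor's clinicians intend the narrower rule:** change 1.4.2 to the wording of 3.2.5, and add a justification for the 90 mmHg threshold at a single 20 uL/kg bolus.

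Either way the cost is one amendment to one criterion or one sentence. The broader rule would screen out about 0 to 1 additional woman per 60 under the stated assumption. Endpoint, sample size and analysis stay as they are.

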#### *Hypersensitivity Reactions*

The real risk of perflutren in our study is to the small number of potential patients with undiagnosed allergy to perflutren. Post-marketing reports have included anaphylactoid events and other serious but non-fatal adverse reactions, typically within 30 minutes of drug administration (see the package insert, and section 6.1.5 for additional information. In order to avoid a potentially fatal event, EpiPen® (epinephrine) injections will be kept near the US machine for all patients.

*High Ultrasound Mechanical Index (MI)*

High ultrasound MI values may cause microsphere cavitation or rupture and lead to ventricular arrhythmias. In addition, end-systolic triggering with high mechanical indices has been reported to cause ventricular arrhythmias.

*Use in Patients with Known Breast Lesions*

US contrast agents including perflutren should carry no additional risks in patients with a known breast lesions, as they are cleared by the lungs. The phospholipid component of perflutren lipid microspheres are thought to be metabolized to free fatty acids, while the octafluoropropane (OFP), as a stable gas, is not metabolized. In a small (n=8) pharmacokinetic study in healthy subjects, OFP was undetectable after 10 minutes in most subjects either in the blood or expired air, with a mean half-life of 1.3 minutes (Definity® Prescribing Information) .

**1.5 Rationale**

One main limitation to the widespread use of contrast enhanced ultrasound clinically has been the lack of availability of state-of-the art contrast imaging approaches available to clinicians. However, contrast ultrasound will likely become far more widespread as new imaging techniques, such as acoustic angiography, demonstrate their usefulness and become available on commercial ultrasound systems. We propose to evaluate a novel ultrasound method that could potentially improve the sensitivity and specificity of traditional breast ultrasound. Increasing the accuracy of diagnostic imaging in high risk patients could provide substantial clinical benefit by improving diagnosis, preventing over-treatment, and reducing healthcare costs.

LCCC1405 is designed to compare the sensitivity and specificity of contrast enhanced ultrasound (acoustic angiography) to the sensitivity and specificity of conventional ultrasound in women scheduled to undergo a biopsy based on pre-study imaging results. The gold standard for sensitivity and specificity, then, will be based on pathological results. The Breast Imaging Reporting and Data System (BIRADS) is used by radiologists who read mammograms, ultrasounds and MRIs to indicate their level of suspicion of the possibility of breast cancer. Scores range from 0 to 6, with scores of 4-5 indicating suspicious results, while 6 indicates an existing diagnosis of breast cancer. This study is limited to women with a score of 4-5 based on pre-study imaging.

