3.1.1 Women  $\geq 18$  years old

3.1.2 Scheduled for breast core needle or surgical biopsy of at least one breast lesion based on suspicious breast lesion (BIRADS score of 4 or 5) from pre-study SOC imaging studies

3.1.3 Center of suspicious lesion is not deeper than 1.5 cm.

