### 10.1 Sample Size and Accrual

Per the revision in increased Perflutren dose, we have updated our sample size statistics as follows.

For power calculation, the null hypothesis is that the specificity of acoustic angiography system is the same as the standard of care (b-mode ultrasound), which is assumed to be 70%. (We will determine the specificity of b-mode ultrasound during the trial to confirm that the 70% represents the specificity in the hands of UNC radiologists) Under the alternative, we expect that the specificity of the new device is at least 90%. The specificities are measured relative to pathological diagnosis as the reference standard. With 60 lesions and 5 readers, where we anticipate that roughly half will be malignant, assuming the correlation from the same patient to be 0.5 and the readers to read different patients independently, the power to see specificity at least larger than 90% is 98% at the significance level 0.05 using one-side test. With 50 lesions (half are benign), the power to see specificity of 90% is >96%; with 25 lesions (about 13 are benign), this power becomes 72%. The power to reject the null hypothesis is 98%. Although we will study both sensitivity and specificity, our power calculation is based on specificity, which is the primary interest.

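### The 70% b-mode specificity is not justified for a cohort enrolled on BI-RADS 4-5, the trial cannot confirm it there, and the 98% power does not cover the planned in-study comparison

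*Combined protocol and SAP*

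**What the plan says.** **Who is enrolled.** Inclusion criterion 3.1.2 requires a biopsy scheduled for a "suspicious breast lesion (BIRADS score of 4 or 5) from pre-study SOC imaging studies". Section 1.5 repeats the restriction: "This study is limited to women with a score of 4-5 based on pre-study imaging". The score need not come from ultrasound, because section 1.5 says that BI-RADS "is used by radiologists who read mammograms, ultrasounds and MRIs to indicate their level of suspicion".

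**Where 70% comes from.** Section 1.2 says that "while breast ultrasound is highly sensitive (96%), it is less specific (70%), resulting in a high false positive rate". It names no population for these figures and goes on: "This results in unnecessary biopsies with associated complications".

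**How 70% is used.** In section 10.1 the null is that the specificity of acoustic angiography is "the same as the standard of care (b-mode ultrasound), which is assumed to be 70" percent. The alternative is at least 90%, tested one-sided at 0.05. B-mode specificity will also be measured during the trial "to confirm that the 70% represents the specificity in the hands of UNC radiologists". Stated power is 98% with 60 lesions, above 96% with 50 and 72% with 25.

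**What is analysed.** Section 10.2.1 estimates sensitivity and specificity for both modalities in the enrolled patients, averages over five readers, and gives bootstrap-based confidence intervals for the differences. Readers score from -2 to +2, and only +1 or +2 counts as malignant. Under section 11.4 the images that contributed to the biopsy decision go into the reader study. Section 4.3.2 makes a second conventional b-mode acquisition on a clinical system optional.

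**The concern.** Benign lesions that standard imaging correctly called benign never enter this study. If ultrasound produced the suspicious call, the enrolled benign lesions are drawn from those that ultrasound got wrong, and a second b-mode reading of them should do worse than in unselected benign lesions. Acoustic angiography took no part in selection and may be penalised less. Re-reading the very images that led to biopsy would strengthen the effect.

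Three things are at stake. The 70% may not describe the comparator in these lesions. Part of an observed specificity gain could come from selection, and section 10.1 names specificity as the measure of main interest. The quoted power also belongs to a test against a constant, while the analysis section compares two estimates from the same study. No section discusses the selection effect.

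**Working it through.** **1. Reproducing the stated power.** Inputs from section 10.1: null 0.70, alternative 0.90, one-sided 0.05, five readers, same-patient correlation 0.5, and 30, 25 or 13 benign lesions.

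Effective n = benign × 5 / (1 + 4 × 0.5), which gives 50, 41.7 and 21.7.

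Power = Φ((0.20 − 1.645·√(0.7·0.3/n)) / √(0.9·0.1/n)).

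For n = 50: (0.20 − 0.1066)/0.0424 = 2.20, so 98.6%. The other two give 96.3% and 72.3%. All match the plan (98%, above 96%, 72%). The calculation is a one-sample test against a fixed 70%, with no sampling error for b-mode.

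**2. Power for the comparison in 10.2.1.** Both specificities are now estimated. Let r be the correlation between the two modalities' reader-averaged results on the same lesion. The documents give no value, so r is an assumption.

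Var(difference) = [p₁q₁ + p₂q₂ − 2r·√(p₁q₁p₂q₂)] / 50, and power = Φ(0.20/SE − 1.645).

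For 70% vs 90% at r = 0: SE = √((0.21 + 0.09)/50) = 0.0775, and Φ(2.58 − 1.645) = 83%. A pooled null variance gives 81%.

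| b-mode vs angiography | r = 0 | r = 0.25 | r = 0.5 |
|---|---|---|---|
| 70% vs 90% | 83% | 90% | 97% |
| 50% vs 70% | 67% | 78% | 90% |

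**3. Dependence on the constant.** Against a fixed 70% with n = 50, the chance of rejection is 45% if angiography's specificity in these lesions is 80%, 5% at 70% and 0.1% at 60%, whatever b-mode achieves in the same lesions.

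**4. Can the trial confirm 70%?** Near 70%, the 95% half-width for b-mode is 1.96·√(0.21/50) = 12.7 points, and the estimate applies only to biopsied BI-RADS 4-5 lesions. Agreement or disagreement with 70% there says nothing firm about ultrasound in general.

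**5. Possible size of the selection effect (illustration).** Assume that both modalities have 70% specificity in all benign lesions (false-positive rate p = 0.30) and that enrolled lesions were called positive on ultrasound. With correlation ρ between the selecting reading and the study reading, specificity among the selected is 1 − [p² + ρp(1 − p)]/p.

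- b-mode: 35% at ρ = 0.5 (a value borrowed from 10.1, where it describes ratings of the same patient), 49% at 0.3.
- Angiography: 52.5% at ρ = 0.25 (assumed), 70% at 0, 35% at 0.5.
- Difference with b-mode at ρ = 0.5: 17.5 points, 35 points and 0 respectively. If half the lesions were ultrasound-selected, 17.5 becomes 8.8.

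A bivariate-normal latent model is a second illustration. With latent correlation 0.5 to 0.8 for b-mode and 0.3 for angiography, b-mode specificity is 48% to 30%, angiography 57%, and the spurious gain about 10 to 28 points (5 to 14 if half were ultrasound-selected).

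**6. A different reading threshold.** Suppose the study cut-off has a 10% false-positive rate in unselected benign lesions (assumed). The formula becomes 1 − [0.3·0.1 + ρ·√(0.21·0.09)]/0.3, giving b-mode specificity of 76% at ρ = 0.3 and 67% at ρ = 0.5.

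**7. Sensitivity.** Cancers missed by pre-study imaging are not enrolled either. In the latent model, a b-mode sensitivity of 96% rises to about 97-98% at correlation 0.5 to 0.8.

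**The case against.** A reader might infer that b-mode specificity must fall below 70% here, perhaps to 35%, and that the whole comparison is tilted against b-mode. The documents do not support that.

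- Selection may rest on mammography, ultrasound or MRI, and the ultrasound share is not given. If no lesion was selected by ultrasound and errors are independent, or if both modalities correlate equally with the selecting read, the spurious gain is zero.
- Readers do not repeat the BI-RADS call. Step 6 shows that a stricter cut-off can leave b-mode near 70%.
- The 0.5 is borrowed from another use and the 0.25 has no source, so 35% and 17.5 points are illustrations, not estimates.
- Sensitivity is also primary, and there selection helps b-mode.
- Against the fixed 70%, selection makes success harder. Angiography at 52.5% would reject with probability below 0.01%. A spurious gain can arise only in the in-study comparison, which does not use 70%.

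It can also be said that the protocol openly restricts itself to women scheduled for biopsy and plans to measure b-mode rather than rely on 70%. That is fair: the trial can validly estimate both specificities in referred lesions and can show that the planning value was wrong for them.

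These points remove any definite size and any claim of a general tilt. They do not supply a justification for 70% in this cohort, they do not make an in-study estimate a confirmation of a general figure, and they do not make the 98% apply to the comparison in 10.2.1.

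**Conclusion.** The point holds in limited form. All enrolled benign lesions were called suspicious beforehand, and the plan carries 70% into that cohort without justification. This cohort cannot confirm it as a general figure.

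B-mode specificity is expected to be lower to the extent that ultrasound drove selection, and more so if the selecting images are re-read. The in-study specificity difference could then favour angiography by selection alone. The size cannot be computed from the documents: the illustrations span 0 to 35 points, against a planned effect of 20. For sensitivity the direction reverses.

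The firmest finding is on power. The 98% is for a one-sample test against a constant. For the planned comparison of 70% with 90% it is about 83% to 97% over cross-modality correlations of 0 to 0.5, and 67% to 90% for the same 20-point gain from 50%. These figures keep the plan's effective n of 50 and one-sided 0.05.

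**What to change.** - **Section 10.1:** delete the statement that the trial will confirm 70%. Restate power for the paired in-study difference over a range of b-mode specificities and cross-modality correlations, as in the table above.
- **Section 10.2.1:** define sensitivity and specificity as conditional on BI-RADS 4-5 referral, and limit the conclusion to women already referred for biopsy.
- **Section 4.5:** from the records already under review, abstract which pre-study modality or modalities were suspicious. More than one may apply, since ultrasound can follow mammography.
- **Reporting:** give the specificity difference for ultrasound-suspicious lesions and for the others, descriptively only. With about 15 benign lesions per group (an even split, assumed), effective n is 15 × 5/3 = 25, and the 95% half-width for one modality near 70% is 1.96·√(0.21/25) = 18 points. That cannot separate selection from benefit.

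The cost is a less favourable stated power, one abstracted field, one descriptive table and a narrower claim. Enrolment does not change.
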